In an Egyptian study conducted by Radi et al. in 2021 on 60 primary molars, the mean survival rate of SMART restorations was 11.2 months higher than that restored with ART restorations, within a follow-up period of 12 months. Although there was a statistically significant decrease in all the tested clinical criteria success rate (spontaneous pain,

mobility, sensitivity to percussion and sinus or swelling) within both groups, with ( $P$ -value <0.001, effect size = 0.367) for the group treated with ART and ( $P$ -value <0.001, effect size = 0.187) for the group treated with SMART (Radi et al., 2021).

In China, a study was conducted by Jiang et al. in 2019 on 194 children, in which 101 children received SMART and 93 received ART. At 24-month follow-up, there was no significant difference between the ART restoration success rates of the two study groups ( $p > 0.05$ ). The success rate of these restorations was affected by the class of these restorations: Class I restorations had the highest success rate (~50 %), followed by Class V (~35 %), Class II (~15 %), and Class III (<10 %). Besides, the meantime used to place SMART restorations was shorter than that in ART restorations with 4.8 and 5.1 mins respectively ( $p = 0.006$ ).

In the same study, parents were asked to rate their satisfaction with their child's teeth using a 5-point scale (5=very satisfied, 1=very dissatisfied), and the Chinese version of the Early Childhood Oral Health Impact Scale (C-ECOHIS) was used to assess the children's OHRQoL before and 6 months after the restorative treatment. At the 6-month follow-up, the mean parental satisfaction score regarding their child's dental health status increased significantly ( $p<0.001$ ) from  $2.2 \pm 0.7$  to  $2.8 \pm 1.0$  in the SMART group and from  $2.3 \pm 0.8$  to  $2.7 \pm 0.9$  in the ART group. However, no significant changes ( $p>0.05$ ) in C-ECOHIS scores were found in either of the two groups after ART restoration placement (Jiang M et al., 2019).

There is a lack of clinical trials comparing ART and SMART restorations. Thus, it is suggested to compare the clinical outcome of both techniques and their impact on oral health related quality of life in preschool children.

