### **Study Sampling:**

#### **• Size formula**

The sample size was specified by using the G power test, assuming a statistical level of significance of 5% and power 80% with normal distribution, and 0.367 effect size calculated from means and standard deviation of 2 groups obtained from a previous study (Jiang et al., 2021). The original sample size will be 64 molars, and will be increased up to 80 with a possible dropout.

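### The 0.367 effect size behind the sample size is described in two conflicting ways, and no SMART-versus-ART data in the documents give it, so the 80% power claim is unsupported

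*Combined protocol and SAP*

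**What the plan says.** Under Study Sampling, Size formula, the plan sizes the trial "assuming a statistical level of significance of 5% and power 80% with normal distribution", using a "0.367 effect size calculated from means and standard deviation of 2 groups obtained from a previous study". It cites a 2021 source and concludes: "The original sample size will be 64 molars, and will be increased up to 80 with a possible dropout". It does not name the effect size metric, the outcome, the test or whether the test is one- or two-sided.

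The Introduction uses the same three-decimal value for something else. For an Egyptian study of 60 primary molars followed for 12 months, it reports a "statistically significant decrease in all the tested clinical criteria success rate" within both groups, with "effect size = 0.367) for the group treated with ART" and "effect size = 0.187) for the group treated with SMART".

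The Introduction also describes a 24-month trial in 194 children. Of restoration success it says that "there was no significant difference between the ART restoration success rates of the two study groups", and it gives no effect size for that comparison.

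**The concern.** A sample size for comparing two techniques needs a planning value for the difference between them. Size formula presents 0.367 as that kind of value. The Introduction gives one figure per arm, each with its own p-value, as the size of the decline inside that arm. A change over time within one arm is not a contrast between arms, and the first cannot be turned into the second without further data.

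This value is the only stated justification for 64 molars and for the 80% power. If no SMART-versus-ART effect lies behind it, a null result could be read as coming from a trial with adequate power against a known difference, when nothing in the documents shows that.

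**Working it through.** **1. Source and meaning, side by side**

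| | Size formula | Introduction |
|---|---|---|
| Value | 0.367 | 0.367 (ART), 0.187 (SMART) |
| Source | a 2021 source | the Egyptian study, 60 molars, 12 months |
| Contrast | means and SDs of two groups | decline within each arm |
| Metric | not stated | not stated |

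The 2021 source is cited elsewhere in the Introduction only for definitions of minimal intervention dentistry and ART. It is not in the reference list, which has a 2020 report of a 24-month trial by the same first author.

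**2. Do any two-group data in the documents give 0.367?** The only means and SDs for both techniques are parental satisfaction scores. At 6 months they are 2.8 (SD 1.0) for SMART and 2.7 (SD 0.9) for ART:

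d = (2.8 − 2.7) / √((1.0² + 0.9²)/2) = 0.1 / 0.951 = 0.105.

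This is not 0.367, and the outcome is different.

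**3. Reproducing the plan's figure.** Inputs from Size formula: 5% level, 80% power, effect 0.367, 64 molars. Assumptions: two-sided test, 1:1 allocation, and 64 molars forming 32 within-child pairs under the split-mouth design. Power is taken from the noncentral t distribution.

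| Reading of 0.367 | Noncentrality with 64 molars | Critical t | Power | Needed for 80% |
|---|---|---|---|---|
| Two-sample d, 32 per arm | 0.367 × √(32/2) = 1.468 | 1.999 (62 df) | 30% | 118 per arm |
| Paired standardised difference, 32 pairs | 0.367 × √32 = 2.076 | 2.040 (31 df) | 52% | 61 pairs |
| Cohen's f for two groups (d = 2 × 0.367 = 0.734), 32 per arm | 0.734 × √(32/2) = 2.936 | 1.999 (62 df) | 82% | 31 per arm |

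With 80 molars, the two-sample d reading gives 37% (40 per arm). The paired reading gives 62% (40 pairs: 0.367 × √40 = 2.321, critical t 2.023).

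The f reading comes close to the plan: 62 molars in total with a t-test and 64 with a Mann-Whitney test. A paired Wilcoxon test also returns 64, but that is 64 pairs, or 128 molars. Read as Cohen's w in a 1-df chi-square test, 0.367 needs 59 molars in total. However, w is built from proportions, which does not fit a value said to come from means and SDs.

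The dropout step is consistent with 20% loss: 64 / (1 − 0.20) = 80.

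**4. What the planned size can detect.** At 80% power, 32 pairs detect a paired standardised difference of 0.512 (0.512 × √32 = 2.896), and 40 pairs one of about 0.455 (0.455 × √40 = 2.878).

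On the success scale, with assumed rates, a normal approximation and pairing ignored, 32 molars per arm reach 80% power for gaps such as 50% versus 83% or 60% versus 90%.

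**The case against.** The strongest reply is that Size formula says plainly that the value was calculated from two groups in a named source, and that source cannot be inspected here. A reader might infer from the three-decimal match that the planning value was copied from the ART arm of the Egyptian study. That is likely, but the documents do not establish it. The missing reference is weak evidence either way, because citation years are loose elsewhere: the 24-month trial is dated 2019 in the text, while the listed 24-month trial by the same first author is dated 2020. This part of the reply stands, so the point is a conflict between two sections, not a proven misattribution.

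It can also be said that 64 is reproducible, and it is if 0.367 is Cohen's f. That rules out calling the figure an arithmetic error. It does not support the input, because the metric is not stated and an f value would still need a between-technique source.

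A reader might also subtract the SMART figure from the ART figure and treat the remainder as the between-arm effect. The documents do not support this: they give no metric for either figure, and within-arm changes do not convert in that way.

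Finally, the background does contain a between-technique result. The Egyptian study is reported as showing restoration survival 11.2 months higher with SMART. That gives some rationale for the comparison, but it comes without an SD or effect size and is not a difference in 6-month success.

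**Conclusion.** The concern holds as a contradiction over the source and meaning of 0.367, together with an unstated metric and no SMART-versus-ART data in the documents that give the value. The 80% power claim for 64 molars is therefore unsupported. Its size depends on the reading: about 30% as a two-sample standardised difference, 52% as a paired one (62% with 40 pairs), and about 82% as Cohen's f. These figures assume a two-sided 5% t-test on a normally distributed outcome. They show how much hangs on the missing metric and do not estimate the trial's true power. The primary outcome is coded restoration success, compared between techniques with Fisher's exact test, so none of them is the power of the planned test.

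A reader might go further and conclude that the trial is underpowered or needs a particular larger number of molars. The documents give no between-technique effect on success, so neither follows. The treatment comparison and its confidence interval do not depend on where 0.367 came from. What is affected is the stated justification and how a null result would be read.

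**What to change.** In Size formula:

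- Either cite the between-technique means and SDs, the outcome and the metric that give 0.367, with the source added to the reference list, or remove 0.367 as a between-group effect. Make the account agree with the Introduction.
- State a SMART-minus-ART difference in 6-month restoration success as the planning value, labelled as an assumption if no source gives one.
- Restate the power, or the detectable difference, of the planned 32 to 40 pairs for that outcome, using a method that respects the pairing. Name the test and whether it is one- or two-sided.
- Withdraw the 80% figure if it is not met.

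The cost is the rewriting of one paragraph and, probably, a less favourable stated power. Whether the number of molars should change cannot be judged until a between-technique planning value is given.

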#### **• Randomization**

Teeth will be randomly assigned to receive either SMART or ART technique, using a website (<https://randomization.com/>)

#### **• Grouping**

- **Group A** the teeth will be restored by ART using high viscosity glass ionomer cement (GC Fuji IX )
- **Group B** the teeth will be treated with silver diamine fluoride 38%, and then restored by high viscosity Glass Ionomer cement (Fuji IX), both according to manufacturer instructions.

- **Inclusion Criteria:**

- Generally healthy children of ages 3 to 6 years old, who have at least 2 bilateral decayed primary molars with occluso-proximal carious dentin lesions (scores 4 or 5) according to the International Caries Detection and Assessment System (ICDAS II)
- Children with negative (Rating 2) and positive (Rating 3) behavior, according to Frankel's behavior rating scale

- **Exclusion Criteria:**

- Children with systemic diseases/conditions
- Children with definitely positive and negative behavior
- Teeth with signs of pulpal pathology (abscess, fistula, mobility)
- Teeth with very deep cavities
- Teeth with signs of irreversible pulpitis

- **Ethical Approval:**

Written informed consent should be signed by patients' parents before participation in the study.

### **Materials:**

- **Silver Diamine Flouride 38%** (Advantage Arrest Silver Diamine Flouride 38%)
- **Glass Ionomer Cement**, Fujji IX GC (powder and liquid)

### **Methods:**

#### **I-Application of ART and SMART restorations:**

- a-Base line Periapical X-Rays when necessary
- b-Oral Prophylaxis
- c-Partial Isolation using saliva ejectors and cotton rolls
- d-Application.

**For Group A** the soft caries will be removed by sharp excavators and the cavity will be restored by Fuji IX GC (powder and liquid), according to the manufacturer's instructions.

**For Group B** the soft caries at the superficial walls will be removed and the teeth will be treated with silver diamine fluoride 38% for 1 minute, using micro-brushes, then dried and restored by Fuji IX GC. (Also in this group, soft caries at the superficial wall must be removed before placement of SDF and GIC)

## **II-Baseline and 6 months Assessment of ORQoL**

The Early Childhood Oral Health Impact Scale (ECOHIS) scales measures the Oral Health-Related Quality of Life (OHRQoL) of preschool children and their families. It consists of 13 items, covering six domains in two sections (Table 1). The child's impacts section contains 4 domains: symptom (1 item), function (4 items), psychology (2 items) and self-image and social interaction (2 items). The family's impacts section contains 2 domains: parental distress (2 items) and family function (2 items). The response categories for each question are rated on a 5-point Likert scale to record how often an event has occurred during the child's life: 0 = never, 1 = hardly ever, 2 = occasionally, 3 = often, 4 = very often, and 5 = don't know (Pahel et al.,2007).

The English version of the ECOHIS was translated into Arabic using the well-recognized forward-backward translation technique. As with the English version, response options for Arabic Early Childhood Oral Health Scale (A-ECOHIS) (Table 2) are rated on a 5-point Likert scale as follows: 0 = never, 1 = hardly ever, 2 = occasionally, 3 = often, 4 = very often, and 5 = don't know (Farsi et al.,2017).

At baseline, parents will be asked to complete a questionnaire that consists of the Arabic version of Early Childhood Oral Health Scale (A-ECOHIS) (Table 2). After a 6- month follow-up period, parents will be assessed and asked to complete the same form of the baseline questionnaire.

**Table 1**

		Never 0	Hardly Ever 1	Occasionally 2	Often 3	Very Often 4	Don't Know 5
Child impact	How often has your child, because of dental problems or the need for dental treatment:						
	1) ...had pain in the teeth, mouth or jaws?						
	2) ...had difficulty drinking hot or cold beverages?						
	3) ...had difficulty to chew food?						
	4) ...had difficulty for pronouncing any words?						
	5) ...Missed pre-school or day-care?						
	6) ...had difficulty sleeping?						
	7) ...been annoyed or bad-tempered?						
	8) ...avoided laughing or smiling when around other children?						
	9) ...avoided talking?						
Family impact	How often have you or another family member, due to dental problems or dental treatment of your child:						
	10) ...felt upset?						
	11) ...felt guilty?						
	12) ...had to take hours or days off work?						
	13) ...had the family's economic situation affected?						

## **Outcome Measurements:**

The primary outcome measure in this clinical study is the success of the ART restorations placed. The children will be examined 6 months after placement of ART restorations (Jiang et al., 2016).

The same instruments used in the baseline examination will be used in the follow-up examinations. The status of the restorations and restored teeth will be assessed and recorded using codes and criteria commonly adopted in previous clinical studies of ART restorations (Lo et al., 2007).

0 = restoration present, no caries, no marginal defects, or wear

1 = restoration present, no active caries, slight defects or wear not greater than 0.5 mm

2 = restoration present, marginal defects greater than 0.5 mm

3 = restoration present, wear greater than 0.5 mm

4 = restoration present, active caries found associated with the filling

5 = restoration missing, no active caries, surface hard to gentle probing

6 = restoration missing, active caries found, surface soft to probing allowing penetration of the tip of a blunt probe

7 = tooth with signs of pulpal pathology

8 = tooth missing, extracted due to caries

9 = tooth naturally exfoliate

## **Statistical Analysis:**

Data analysis was carried out by using the statistical software SPSS (version 28, IBM SPSS statistics, USA. Based on the results of the Shapiro-Wilk test, most of the data were determined to follow a normal distribution. The significance level was set at  $p \leq 0.05$ . The qualitative data were presented as frequencies and percentages, whereas the quantitative data were presented as median, range, mean, and standard deviation values. Paired Samples

t-Test was used to compare the means of two related groups, it was used to assess changes in ECOHIS scores at baseline and after intervention. Fishers exact test was used to compare the outcomes between ART and SMART at a single time point. Categorical data like the relation between the success rate of both treatments and the type of the cavity was analyzed by using the Chi-Square Test of Independence. The significance level was set at  $p \leq 0.05$ .

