## **The Null Hypothesis**

There is no difference between SMART and ART in arresting caries, success, and retention rate as well as their impact on the oral health-related quality of life.

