## **Materials and Methods**

### **Study design:**

Randomized clinical trial using split-mouth design technique.

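### The primary ART versus SMART comparison uses Fisher's exact test for independent teeth in a split-mouth trial, which is conservative and gives up power when outcomes within a child are positively correlated

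*Combined protocol and SAP*

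**What the plan says.** The Study design section describes a "Randomized clinical trial using split-mouth design technique". The inclusion criteria, under Grouping, require each child to have "at least 2 bilateral decayed primary molars with occluso-proximal carious dentin lesions". Under Outcome Measurements, "The primary outcome measure in this clinical study is the success of the ART restorations placed"; it is coded tooth by tooth at 6 months.

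For comparing the treatments, the Statistical Analysis section says "Fishers exact test was used to compare the outcomes between ART and SMART at a single time point". The only paired method in the plan is in the same paragraph: a paired "t-Test was used to compare the means of two related groups", applied to ECOHIS before and after treatment. A further analysis relating "the success rate of both treatments and the type of the cavity was analyzed by using the Chi-Square Test of Independence" also takes teeth as independent. McNemar's test, conditional logistic regression, GEE and mixed models are not mentioned anywhere.

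**The concern.** Two molars in one mouth share diet, hygiene, saliva and behaviour, so their outcomes can be expected to correlate positively. A split-mouth design exploits this, because what the two teeth share cancels from the within-child difference. Fisher's test discards that information. It uses a variance suited to unrelated teeth, which is too large for paired ones.

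The error runs towards missing a true difference. The stated null hypothesis is "There is no difference between SMART and ART in arresting caries, success, and retention rate", so a non-significant result from a test that is too conservative could be read as evidence that the techniques are equivalent. The comparison affected is the one for the primary outcome.

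The inclusion criterion sets a minimum of two molars, not a maximum. A child with more than two treated teeth forms a cluster that a simple paired test does not cover either.

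**Working it through.** **Inputs from the plan.** Size formula section: 5% significance, 80% power, effect size 0.367, and "The original sample size will be 64 molars, and will be increased up to 80 with a possible dropout". The dropout step reproduces: 64/(1 − 0.20) = 80. The 64 reproduces as 64 pairs (two-sided Wilcoxon signed-rank test, standardised paired difference 0.367), or as 64 molars in total (Mann-Whitney test) if 0.367 is read as Cohen's f, that is d = 0.734. The plan does not say which. Below, 64 and 80 molars are taken as 32 and 40 pairs, one per child.

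**Assumptions.** Success rates, within-child correlation φ and two-sided testing are not in the documents. Rates of 60% versus 85% and 70% versus 90% are used, with φ = 0, 0.2 and 0.3. The largest feasible φ is 0.514 for the first pair of rates and 0.509 for the second.

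**Variance.** For n pairs with success probabilities p₁ and p₂ and qᵢ = 1 − pᵢ, the variance of the difference is [p₁q₁ + p₂q₂ − 2φ√(p₁q₁p₂q₂)]/n. An independent-samples test omits the last term. With equal rates, the true variance is (1 − φ) times the one assumed: 0.8 times at φ = 0.2 and 0.7 times at φ = 0.3.

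**Cell probabilities.** P(both succeed) = p₁p₂ + φ√(p₁q₁p₂q₂). For 60% versus 85% at φ = 0.2 this is 0.510 + 0.2 × 0.175 = 0.545, which leaves 0.055 ART only, 0.305 SMART only and 0.095 neither. Every possible paired table was enumerated exactly, rejecting at p ≤ 0.05.

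**Power (%), Fisher / exact McNemar / mid-p McNemar**

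| Pairs, rates | φ = 0 | φ = 0.2 | φ = 0.3 |
|---|---|---|---|
| 32, 60% vs 85% | 53 / 50 / 59 | 53 / 59 / 69 | 53 / 66 / 75 |
| 32, 70% vs 90% | 41 / 39 / 49 | 40 / 46 / 58 | 39 / 51 / 63 |
| 40, 60% vs 85% | 64 / 63 / 71 | 66 / 72 / 80 | 66 / 79 / 85 |

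Fisher against exact McNemar is the like-for-like contrast. The paired test changes power by −1 to −3 points at φ = 0, +6 to +7 at 0.2 and about +12 at 0.3. The mid-p column also gains from being less discrete.

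**Type I error (%), 70% in both arms, 32 pairs, same order:** 2.8 / 2.6 / 4.5 at φ = 0; 1.4 / 2.3 / 4.2 at 0.2; 0.9 / 2.1 / 4.1 at 0.3. Part of Fisher's shortfall from 5% is discreteness, since it is already at 2.8% with no correlation. The further fall to 0.9% comes from ignoring the pairing.

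**Pairs needed for 80% power, Fisher vs exact McNemar** (smallest n from which power stays at or above 80% up to n = 90)

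| Rates | φ = 0 | φ = 0.2 | φ = 0.3 |
|---|---|---|---|
| 60% vs 85% | 56 vs 57 | 53 vs 46 | 51 vs 42 |
| 70% vs 90% | 69 vs 71 | 65 vs 58 | 64 vs 52 |

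**Constructed example, 40 pairs:** 24 both succeed, 10 SMART only, 2 ART only, 4 both fail. Success is 34/40 against 26/40, with φ = (24×4 − 10×2)/√(34×6×26×14) = 76/272.5 = 0.28.
- Fisher: p = 0.069.
- Exact McNemar: 2(1 + 12 + 66)/4096 = 0.039.
- Mid-p: (158 − 66)/4096 = 0.022.
- Paired risk difference: (10 − 2)/40 = 20 points, Wald 95% CI 0.20 ± 1.96√(12 − 64/40)/40, or 4 to 36 points.

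**The case against.** **Allocation.** The conservative direction requires each child's two molars to go to opposite treatments. The Randomization section says only that teeth are assigned at random. If teeth were randomised singly, Fisher's test would sit near its usual level: in simulation, about 2.5 to 2.8% type I error with 40 children, two teeth each, 70% success and correlation 0.2 to 0.3. McNemar's test could not use children with both teeth in one arm. This condition stands and should be stated. It does not rescue the plan, because split-mouth means that the two sides of a child receive different treatments. With m teeth per arm in each child, the variance ratio is 1 + (m − 1)ρ_within − mρ_between, which stays below 1 under a common positive correlation.

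**Size.** The gain is modest, rests on assumed rates and correlations, and becomes a small loss at zero correlation. The example was built to fall on either side of 0.05. Exact McNemar does not reach 80% power in any tabulated scenario (39 to 66% at 32 pairs, at most 79% at 40). All of this is fair. The paired test recovers what the design offers but does not guarantee the planned power, which in any case was calculated from means and standard deviations, not proportions.

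**Conservatism is safe.** A conservative test protects against false positives. It gives no protection where a non-significant result may be taken to support a null of no difference.

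**The cavity-type chi-square test.** Here the direction can reverse. If both molars of a child share a cavity type, positive correlation inflates false positives: in simulation with 40 children, 70% success and types split evenly between children, to about 7% at correlation 0.2 and 8 to 8.5% at 0.3. The statement that false positives are not inflated therefore applies to the Fisher comparison only. This adds to the case for a clustered analysis of cavity type.

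**Conclusion.** The concern holds. The test named for the primary comparison does not match the declared design, and nothing elsewhere in the plan supplies a method that does. With one ART and one SMART tooth per child and positive correlation, Fisher's test is conservative. In the scenarios tried, it gives up 6 to 7 points of power at correlation 0.2 and about 12 at 0.3, and it gains 1 to 3 at zero. These sizes depend on assumed success rates and correlations; the mismatch between test and design does not. Because it affects the primary outcome and is cheap to correct, it should be corrected before the comparison is reported.

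**What to change.** In the Statistical Analysis section:

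- Replace Fisher's test for ART versus SMART with McNemar's test, choosing exact or mid-p in advance, and report the paired risk difference with its 95% confidence interval. This applies when each child contributes one pair.
- If any child contributes more than two molars, use conditional logistic regression or GEE clustered on child. With 32 to 40 children, GEE needs small-sample-corrected standard errors.
- Define cavity type so that it can vary among eligible teeth, all of which must have occluso-proximal lesions, and analyse it in the same clustered framework.

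As a separate clarification, the Randomization section should state that the two treatments are randomised between sides within each child.

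The cost is small: revised wording, a child identifier on every tooth record, and a rerun if the analysis has been done, as the section's past tense suggests. No extra children or measurements are needed. Two trade-offs remain. McNemar's test drops a pair when one tooth cannot be assessed (for example code 9, natural exfoliation), whereas GEE keeps the other tooth. If the true correlation is near zero, exact McNemar loses 1 to 3 points of power against Fisher.

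### In a split-mouth trial, ART and SMART are compared by an unpaired, unadjusted Fisher test: valid, but it gives up precision, mainly from the pairing and secondarily from tooth-level ICDAS severity

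*Combined protocol and SAP*

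**What the plan says.** The Study design section describes a "Randomized clinical trial using split-mouth design technique". Under Randomization, "Teeth will be randomly assigned to receive either SMART or ART technique"; no stratification or matching is mentioned. The inclusion criteria, under Grouping, admit children "who have at least 2 bilateral decayed primary molars with occluso-proximal carious dentin lesions (scores 4 or 5" on ICDAS II. They do not require the two molars to share a score or a molar type. The Introduction presents ICDAS as grading the potential depth of a lesion, so by the protocol's own account 4 against 5 is a difference in severity.

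For the treatment comparison, the Statistical Analysis section gives one method: "Fishers exact test was used to compare the outcomes between ART and SMART at a single time point". The only tooth-level factor analysed is cavity type, in a separate chi-square test that does not adjust the comparison. No paired test for the restoration outcome, adjusted model or table of ICDAS by arm is planned. The paired t-test in that section is for ECOHIS scores before and after treatment.

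The size of the trial is given as: "The original sample size will be 64 molars, and will be increased up to 80 with a possible dropout".

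**The concern.** A split-mouth design lets each child serve as its own control. That advantage reaches the result only if the analysis is paired, and Fisher's exact test treats the two molars of a child as unrelated.

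Pairing balances what belongs to the child. It does not balance what belongs to the tooth, and lesion severity belongs to the tooth. With few pairs, one arm may by chance receive visibly more score 5 molars. The reader would then have no pre-specified way to judge whether severity explains the result, and an adjustment chosen after seeing the data would be open to challenge.

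**Working it through.** **1. Number of pairs.** The Size formula section gives 64 molars, raised to 80. This fits 64/(1 - 0.20) = 80, although the 20% dropout is not stated. At one pair per child, that is 64/2 = 32 to 80/2 = 40 pairs. The 64 itself comes from "assuming a statistical level of significance of 5% and power 80% with normal distribution, and 0.367 effect size". With a two-sided test it is reproduced as 64 *pairs* (Wilcoxon signed-rank), or as 64 *molars* only if 0.367 is Cohen's f (Mann-Whitney, 32 per arm). If 0.367 is a standardised mean difference, paired-t power is 52% with 32 pairs and 62% with 40, so precision may be scarce.

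**2. Size of a chance severity imbalance.** If a share *q* of *n* pairs differ in score, the SD of the between-arm difference in the share of score 5 is sqrt(*q*/*n*). *q* is not in the documents; 30% to 50% is assumed.

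| Pairs | *q* = 30% | *q* = 50% |
|---|---|---|
| 32 | sqrt(0.30/32) = 9.7 points | sqrt(0.50/32) = 12.5 points |
| 40 | sqrt(0.30/40) = 8.7 points | sqrt(0.50/40) = 11.2 points |

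If score 5 molars succeed 25 points less often (assumed), one SD of imbalance moves the success difference by 0.25 x 8.7 = 2.2 to 0.25 x 12.5 = 3.1 points.

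**3. Comparison with the standard error.** A simulation used 32 and 40 pairs, about 70% success, half of lesions scoring 5, *q* = 20% or 50%, an odds ratio for failure (5 against 4) of 2 or 4, and a within-child SD on the logit scale of 0 or 1.5.
- An imbalance of 10 points or more occurred in 15-22% of trials (*q* = 20%) or 38-44% (*q* = 50%).
- A 10-point imbalance moved the success difference by about 1-3 points, against a standard error of about 8-12 points.
- ICDAS imbalance explained about 1-9% of the variance of the estimated difference.
- With no treatment effect, the mean difference was 0 and Fisher's test rejected in 0.9-3.3% of trials.

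**4. What pairing is worth.** For complete pairs the estimated difference is the same paired or unpaired; what changes is the uncertainty attached to it. In one simulated cell (32 pairs, *q* = 20%, severity odds ratio 2, no treatment effect), the true standard error was 11.4 points without within-child correlation and 9.7 with SD 1.5. That is 1 - (9.7/11.4)² = 28% less variance, against about 1% from ICDAS in the same cell. Fisher's test does not credit this: its null rejection rate fell from 2.8% to 0.9%. At a treatment odds ratio of 3 and SD 1.5, power across cells was 14-22% for Fisher and 19-29% for exact McNemar.

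**5. What adjustment adds.** Let D be the within-child difference in success (SMART minus ART) and X the within-child difference in ICDAS score (-1, 0 or 1). Fit D = a + bX; the intercept a is the adjusted risk difference. Simulated with 32-40 pairs, this held type I error at about 4-6%. At a 25-point severity effect and a 20-point treatment effect, power rose from 26% (Fisher) to 38% with 32 pairs, and from 34% to 47% with 40. Most of that rise comes from pairing and from leaving a conservative exact test. The part due to ICDAS is:

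| Assumed severity effect | Change in precision from adjusting | In pairs, of 40 |
|---|---|---|
| 10 points | loss of 2-4% | -0.8 to -1.6 |
| 25 points | gain of 0-6% | 0 to 2.4 |
| 40 points | gain of 8-20% | 3.2 to 8 |

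**The case against.** A reader might infer that a chance severity imbalance passes straight into the result and so undermines it. The documents do not support that. Teeth are randomised, so the imbalance is part of the random error that the test already allows for; the simulated mean difference is 0 and type I error stays below 5%.

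A reader might also infer that adjustment is free because the score is already on file. Scoring each tooth is unavoidable for eligibility, but the documents do not say that the 4 or 5 is kept as data. Adjustment also loses a little precision if severity hardly matters.

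The strongest case against the point is that it is small. Every size above rests on assumed effects. Entry is already narrowed to occluso-proximal lesions at two adjacent scores, and very deep cavities and teeth with pulpal pathology are excluded, which may favour the lower end of the range. That stands, and it is why severity is the secondary part. The gain from pairing is also conditional: with no within-child correlation and 32 pairs, exact McNemar had 27-28% power against 28-30% for Fisher. But a split-mouth design is chosen because such correlation is expected.

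Three practical objections also stand. The Outcome Measurements section lists codes 0 to 9 without saying which count as success. Children may contribute more than one pair. And the Statistical Analysis section is in the past tense and reports a normality finding, so the data may already have been analysed.

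**Conclusion.** The point holds as one of efficiency, not validity. The planned test matches neither the split-mouth design nor the tooth-level severity that the entry criteria establish. The main loss is the ignored pairing, provided that outcomes of two molars in one child are positively correlated. ICDAS adjustment alone is worth between a 2-4% loss and an 8-20% gain in precision across assumed severity effects of 10 to 40 points, with 0-6% at 25 points. These figures assume 32 to 40 pairs and one pair per child; the documents give no discordance rate, success rate or severity effect. The change is still worth making. It is cheap, it supplies a risk difference with a confidence interval, which the plan lacks, and it settles in advance how a visible severity imbalance will be handled.

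**What to change.** In the Statistical Analysis section:
- Replace Fisher's test with a pre-specified paired ART-SMART comparison. Report the paired risk difference with 95% CI, and say how a child with only one assessable molar is handled.
- Beside it, report the severity-adjusted paired risk difference with 95% CI: the intercept from regressing the within-child difference in success on the within-child difference in ICDAS score. Use child-clustered errors if any child contributes more than one pair.
- Keep each molar's ICDAS score as data and tabulate it by arm.
- State which outcome codes count as success, since both analyses depend on it.

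The cost is one data field per tooth, one table and one regression, with no added children or visits. The downside is about 2-4% lower precision in the adjusted estimate if the score hardly affects success, which is why the unadjusted paired result stays beside it. If outcome data have already been analysed, label the ICDAS adjustment post hoc.
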